1. SUMMARY

Study description: This is a CORE protocol for an adaptive multiregional international global randomized, placebo-controlled trial to evaluate the safety and efficacy of drugs for the treatment of human monkeypox (Phase 3). Each site interested in participating can enroll patients in this international trial and implement the core protocol. This will require commitment to assess the main objectives as defined by the core protocol; enrolling homogenous population (common inclusion criteria); and evaluating the same interventions with the same primary and secondary endpoints. This adaptive design will allow future flexibility in testing several treatments.

Add-on studies Particular countries, or groups of centres may want to collaborate in assessing additional endpoints or to include further measurements or observations and include questions that are locally relevant (add-on trials).

Simplicity of procedures: Within each country or region, the national or regional Principal Investigators invites selected centres and helps them get ethical and regulatory approval and study drugs, then patient recruitment can begin. To facilitate collaboration, patient enrolment and randomisation are simplified, and core variables are collected using standardized definitions and will be sent in real time to a centralized data base (potentially across countries via a cloud-based GCP-compliant platform). All trial procedures are greatly simplified, and minimal paperwork is required. Once consent has been obtained, electronic entry of anonymised details of a few key characteristics of each patient takes only a few minutes. At the end of patient entry, a random treatment allocation is generated using a national (or by a global randomization center).

Quality requirements: centers sending these data should meet quality requirements (to be defined) that make them eligible to be part of the global analysis.

Eligibility: Adults and children (6 years and older) with laboratory-confirmed (PCR) monkeypox illness of any duration (provided that the patient has at least one active, not yet scabbed, lesion), and, who have no contra-indication to potentially study drug.

Consent: Once the information has been explained to patients, obtaining consent takes only a few minutes. An electronic image of the signature page is kept (or, if national regulations forbid this, a note to file), and the printed information and original consent stays with the patient or legal representative.

Data collected electronically immediately before randomisation. These include:

- Country, geographic region of residence, hospital and randomizing doctor
- Confirmation that informed consent was obtained from the patient (or a surrogate/representative)
- Age, sex and (yes/no): HIV, TB, malaria, hypertension, diabetes mellitus, asthma, hepatitis, hyperlipidemia, cancer, heart failure, renal disease, liver disease, chronic obstructive pulmonary disease (COPD), COVID-19, neoplasm, obstructive sleep apnea, obesity, immunosuppressive disorder other than HIV, sickle cell anemia, concurrent bacterial infections such as urinary tract, ear nose and/or throat, pulmonary, central nervous system, skin or gastrointestinal infection, bacteremia/sepsis or other.
- Date of onset of symptoms, date of hospitalization, and (yes/no) current/planned use of a few drugs
- Monkeypox lesions status (yes/no): at least one active, not yet scabbed, monkeypox lesion, other.
- Current symptoms (yes/no): nausea, vomiting, abdominal pain, anorexia, cough, lymphadenopathy, dysphagia, fever, headache, ocular lesions, and buccal ulcers.

- Smallpox vaccination status (yes/no) or presence of vaccination scar (yes/no).
- Risk factors for monkeypox infection (yes/no): recent contact with known monkey pox case, type of contact, residing or visiting an area with an active monkey pox outbreak, animal handling.

Trial entry; randomization: A participant will be considered enrolled beginning from when the informed consent form is signed and randomization to an assigned treatment has occurred. Once enrolled, study drug administration will begin according to study group assignment. Participants will be randomized to one of the experimental treatments (k in number) for which they are eligible (no specific exclusion criteria) or to one of the placebos that correspond (in appearance, dosing interval, and route of administration) to each of those treatments. The randomization ratio will ensure that participants have the same chance of receiving a placebo as they have of receiving each individual treatment for which they are eligible. All participants will also receive local SOC that is standardized at each site according to local/site guidance.

Follow up: Participants will either be hospitalized or outpatients and will undergo frequent clinical and laboratory assessments for safety and efficacy. Day 28 is the final required study visit, but participants may return for an optional visit at day 58 for long-term clinical and laboratory evaluations.

Objectives and endpoints: This CORE protocol will include outpatients and hospitalized patients. It is being designed to test one or more targeted interventions across multiple types of disease stages. Sites may choose to enrol outpatients, hospitalized patients or both.

The primary objective is to evaluate the clinical efficacy, as assessed by time to lesion resolution, of treatment plus SOC versus placebo plus SOC for patients with monkeypox.

The primary endpoint is time to resolution of all lesions¹ (including skin and mucosa), up to 28 days after randomization (assessment every 3-5 days).

For secondary and exploratory endpoints please see section 5.

Safety: Any suspected unexpected serious adverse reactions (SUSARs) that are life-threatening must be reported within 24 hours, as must any other possibly related treatment-related serious adverse events (SAEs).

Study Population

Inclusion criteria

- Adults and children (6 years and older) with laboratory-confirmed (PCR) monkeypox illness of any duration (provided that the patient has at least one active, not yet scabbed, lesion), and, who have no contra-indication to potentially study drug.
- Men and non-pregnant women of reproductive potential must agree to use effective means of contraception when engaging in sexual activities that can result in pregnancy, from the time of enrolment through the end of study participation. Acceptable methods of contraception include the following: hormonal contraception, male or female condom, diaphragm or cervical cap with a spermicide and intrauterine device.

Exclusion criteria

- Current or planned use of another investigational drug at any point during study participation.

¹ **Time to lesion resolution:** lesions of skin and mucosa are crusted, scabs have fallen off and a layer of skin has formed underneath

- Patients who, in the judgement of the investigator, will be at significantly increased risk as a result of participation in the study.
- Specific exclusion criteria for each evaluated drug will be considered.

Pregnant women and special populations will be enrolled in this study if the national principal investigator, the national regulatory authorities, and the ethics committee agree that the benefits of receiving the experimental treatment outweigh its risks, and specifically if they consent to participate after the information on risk and benefits is provided.

Study sites: Study sites will be in geographic locations where cases of monkeypox were reported. Sites will be opened one after another to ensure correct workflow of activities within a site and synchronization of activities between sites later on.

Study intervention: Details regarding dose administration for each evaluated treatment will be added here

Study Duration: The day when the subject is randomized to their assigned treatment arm is denoted as Study Day 1. Screening procedures will occur in the 24 hours prior to randomization (Study Day -1 to 1). Note that there is no Study Day 0. Study Day -1 is the 24-hour day prior to the day of randomization. The first day after randomization is Study Day 2. Subsequent days will be numbered chronologically through Day 58 of study.

Statistical considerations

Primary endpoint analysis: A stratified log-rank test will be used to compare arms with respect to time to lesion resolution², where stratification is by days from onset of symptoms to randomization (≤ 7 days vs > 7 days) and by baseline severity³. Participants with any lesions not scabbed or desquamated at 28 days after randomization will be censored for statistical analysis of this endpoint. Though deaths are expected to be relatively rare, deaths will also be censored at 28 days post-randomization.

Number of participants: The precise rates of clinical and microbiological resolution are uncertain for monkeypox in general, and for the current epidemiological context. The larger the numbers entered the more accurate the results will be. Realistic, appropriate sample sizes may not be estimated at the start of the trial; the numbers that can be entered will depend on the evolution of the outbreak.

Data Monitoring Committee: A global Data Monitoring Committee (DMC) will monitor accumulating efficacy and safety data on an ongoing basis. The mission of the DMC will be to safeguard the interests of study participants and to enhance the integrity and credibility of the trial. The DMC will be asked to recommend stopping the study early for efficacy only when there is clear and substantial evidence of a treatment benefit. The PIs and Sponsors will make decisions about trial continuation based on recommendations received from the DMC.

² **Time to lesion resolution:** lesions of skin and mucosa are crusted, scabs have fallen off and a layer of skin has formed underneath

³ The definition of severity is being discussed.

2. Schema

[figure not shown]

Figure 1. Study Schema.

3. Schedule of Activities

Evaluation/Procedure	Screen	Baseline	Follow-Up		
Day +/- Window	-1 or 1	1	Daily if hospitalized, or every 3 to 5 days for outpatients ^d	28±7 ^a	58±7 ^b
OPERATIONAL AND CLINICAL ASSESSMENTS					
Informed consent	X				
Eligibility (inclusion/exclusion) assessment	X				
Demographics	X				
Medical history	X				
Randomization		X			
Vital Signs		X	X	X	X
Lesion Assessment ^e		X	X		
Record standard-of-care treatments		X	X		
Current symptoms		X	X	X	X
Assessment of AEs/SAEs		X	X	X	X
STUDY DRUG ADMINISTRATION					
Study drug administration		Treatment or placebo following schedule of administration of the drug			
RESEARCH LABORATORY EVALUATIONS					
Monkeypox PCR (blood) with CT	X ^g		Every other day if hospitalized, or every 3 to 5 days for outpatients if in virological sub-study		
Blood for storage		X	Day 14 for outpatients or earlier upon discharge for hospitalized patients (if feasible consider for outpatients)	X	X
Oropharyngeal and rectal lesions swab		X	For hospitalized patients: every other day until discharge; or every 3 to 5 days for outpatients if in virological sub-study		
Skin lesions swab		X	For hospitalized patients: every other day until discharge; or every 3 to 5 days for outpatients if in virological sub-study		

To be included in some sites if locally relevant and feasible

CLINICAL LABORATORY EVALUATIONS ^a					
Malaria rapid test	X				
Glucose (mg/dl)	X	X	Every other day until discharge	X	X
Hemoglobin (g/dL)	X	X	Every other day until discharge	X	X
Hematocrit (L/L)		X	Every other day until discharge	X	X
Creatinine (mg/dL)		X	Every other day until discharge	X	X
Potassium (mmol/L)		X	Every other day until discharge	X	X
Sodium (mmol/L)		X	Every other day until discharge	X	X
eGFR (mL/min/1.73m ²)		X	Every other day until discharge	X	X
AST (U/L)		X	Every other day until discharge	X	X
ALT (U/L)		X	Every other day until discharge	X	X
BUN (mg/dL)		X	Every other day until discharge	X	X
CBC with differential (c/mm ³)		X	Every other day until discharge	X	X
Calcium (mg/dL)		X	Every other day until discharge	X	X
Total protein (g/dL)		X	Every other day until discharge	X	X
C-reactive protein (ug/mL)		X	Every other day until discharge	X	X
Creatinine kinase (U/L)		X	Every other day until discharge	X	X
Total CO ₂ (mEq/L)		X	Every other day until discharge	X	X
Chloride (mEq/L)		X	Every other day until discharge	X	X
Alkaline phosphatase (IU/L)		X	Every other day until discharge	X	X
t-Bilirubin (mg/dL)		X	Every other day until discharge	X	X
Amylase (U/L)		X	Every other day until discharge	X	X

CLINICAL LABORATORY EVALUATIONS ^h					
Albumin (g/dL)		X	Every other day until discharge	X	X
PT (sec)/aPTT (sec)/INR		X	Every other day until discharge	X	X
D-dimer (ng/mL)		X	Every other day until discharge	X	X
Fibrinogen (mg/dL)		X	Every other day until discharge	X	X
Urinalysis, dipstick		X	Every other day until discharge	X	X

Abbreviations: AE, adverse event; ALT, alanine transaminase; aPTT, activated partial thromboplastin time; AST, aspartate transaminase; BUN, blood urea nitrogen; CBC, complete blood count; CO₂, carbon dioxide; CT, cycle threshold; eGFR, estimated glomerular filtration rate; INR, international normalized ratio; PCR, polymerase chain reaction; PT, prothrombin time; SAE, serious adverse event.

^a This study visit will include a +/- 7-day visit window for outpatients and hospitalized participants discharged prior to Day 28. For participants who remain inpatient through Day 28, the visit should take place exactly on Day 28.

^b The Day 58 visit is optional and may be completed in person or by phone. Failure to complete a Day 58 visit will not result in a protocol deviation. Some procedures may not be able to be performed if the visit takes place over the phone.

^c Only for participants who weigh <40 kg. For these participants, weight will be taken each morning before breakfast and used to calculate the study drug dose for that day.

^d Hospitalised participants are eligible for discharge at the discretion of the treating physician; after discharge they will be followed-up every 3 to 5 days. The date of discharge will be documented.

^e During lesion assessments any unresolved lesions in the target assessment region will be counted. While the participant still has unresolved lesions in the target region, assessment of whether there are unresolved lesions on other areas of the body will be optional but preferred. Once all lesions in the target region are resolved, a simplified full body lesion assessment will be done until all lesions are resolved.

^f All baseline assessments should be complete before starting study drug. Administration of the evaluated drug or placebo should be continued if the participant meets the criteria for discharge.

^g Although any positive monkeypox PCR from blood collected up to 48 hours prior to informed consent may be used to establish eligibility, a new specimen must be collected within 24 hours prior to randomization if the prior specimen is more than 24 hours old.

^h With the exception of screening collection of glucose and hemoglobin (both of which are required for determining eligibility), all labs at all time points, though highly desirable, may be waived if not feasible (e.g., due to blood draw volume concerns related to participant weight or due to site logistics), per investigator discretion. Any laboratory tests obtained within 24 hours from randomization for screening purposes do not need to be repeated on day 1.

4. Introduction

Study Rationale

WHO calls for the use of antivirals for the treatment of monkeypox cases within a framework of collaborative research and randomized clinical trial (RCT) protocols with standardized data collection tools for clinical and outcome data to rapidly increase evidence generation on efficacy and safety^{4,5}. This includes a scientific steering committee, common data management, and robust statistical analysis plan to satisfy regulatory requirements. Harmonised data collection for safety and clinical outcome (using WHO Global Clinical Platform for Monkeypox⁶) would represent a desirable minimum in the context of an outbreak such as current one.

A platform trial uses a shared infrastructure, in which various treatments are evaluated using the same 'CORE protocol' and tested against a shared control condition. Moreover, the speed of platform trials might help to accelerate the evaluation of drugs and generate evidence from different subgroups and different geographic locations.

Each site interested in participating can enroll patients in this international trial and implement the core protocol. This will require commitment to assess the main objectives as defined by the core protocol; enrolling homogenous population (common inclusion criteria); and evaluating the same interventions with the same primary and secondary endpoints. There will be an option for countries or regions to complement the core protocol through add-on studies with additional sub-analyses

Ethical and regulatory approvals will be handled by each country's or region's principal investigators. A centralized randomization facility will be available. Data, corresponding to main objectives and core variables will be sent in real time to a centralized data base (using WHO provided platforms); centers sending these data should meet quality requirements (defined a priori) which make them eligible to be part of the global analysis. A statistical analysis plan will be developed. Monitoring of a proportion of data should be possible (by the entity doing the central data collection, or at least overseen by them).

A scientific steering committee and global DSMB will help steer the trial decisions regardless of existence of individual trials ones should be implemented.

⁴ https://cdn.who.int/media/docs/default-source/2021-dha-docs/20220706_monkeypox_external_sitrep_final.pdf?sfvrsn=1b580b3d_4&download=true

⁵ <https://www.who.int/emergencies/disease-outbreak-news/item/2022-DON396>

⁶ <https://www.who.int/tools/global-clinical-platform/monkeypox#:~:text=Global%20understanding%20of%20the%20natural,patient%2Dlevel%20anonymized%20clinical%20data>

5. Objectives and endpoints

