1.1 All-cause mortality within the first 28 days (applied to all patients)

Rationale: all -cause mortality more reliably measured than MPX-specific mortality. Easy to measure, reliable.

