A quality log will be kept documenting any temperature excursions affecting the study agents (less than 15°C and more than 30°C). Temperature excursions outside of this range will be reported, and the log will be made available to the principal investigator, pharmaceutical company, and study pharmacist to establish whether the affected product can be used. All critical issues/conditions relating to the quality of the product will be documented. A destruction log will be available at the site to document the destruction of all expired or damaged product batches.

Concomitant therapies

All concomitant prescription and nonprescription (including over-the-counter, herbal, or traditional) medications taken during study participation will be recorded. For this protocol, a prescription medication is defined as a medication that can be prescribed only by a properly authorized/licensed clinician.

10. Drug discontinuation (which does not imply withdrawal from follow-up)

At all times the patient's medical team remains responsible for decisions about that patient's care and safety. Hence, if the medical team decide any deviation from the randomly allocated treatment arm is definitely appropriate then this should be done, although the patient would remain in the trial and should still be followed for outcomes.

1. Study drug administration should be stopped if the team suspects any serious unexpected drug-related adverse reaction that is life-threatening, and this SUSAR should immediately be reported electronically. The patient will still be followed in the usual way at the end of their time in hospital.
2. Study drug administration should be stopped if the treating physician considers this is definitely in the patients' best interest (including but not limited to life threatening events) or if the patient or a legal representative decide it should be stopped. The patient should still be followed in the usual way at the end of their time in hospital, unless it is decided otherwise (see below).

11. Decision by a patient or legal representative to withdraw from follow-up

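### The final required visit may fall up to 8 days before the 28-day horizon for outpatients and discharged participants, and the schedule marks no lesion assessment at it

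*Protocol*

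**What the plan says.** **Final visit.** The Summary (Follow up) and section 6 make Day 28 the last required visit and Day 58 optional. Section 3, footnote a, sets the timing: "This study visit will include a +/- 7-day visit window for outpatients and hospitalized participants discharged prior to Day 28". For everyone else: "For participants who remain inpatient through Day 28, the visit should take place exactly on Day 28".

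**Day numbering.** Randomization is Study Day 1 and there is no Day 0: "The first day after randomization is Study Day 2" (Summary, Study Duration; section 12).

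**Endpoints.** The Summary defines the primary endpoint "up to 28 days after randomization (assessment every 3-5 days"), and section 13 censors unresolved participants at 28 days. Section 5.2 defines three secondary endpoints over the first 28 days: mortality (item 1.1), hospital admission for outpatients (item 1.2) and complications (item 1.3). Item 1.3 sets complication data collection at baseline and day 28.

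**Schedule.** The row "Lesion Assessment ^e" is marked at baseline and in the follow-up column headed "Daily if hospitalized, or every 3 to 5 days for outpatients". It is blank under 28±7, where vital signs, symptoms and adverse events are marked. Footnote d continues visits every 3 to 5 days after discharge, and footnote e continues lesion assessment until every lesion has resolved.

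**After study drug is stopped.** Section 10 opens by keeping the patient in the trial with outcomes followed. Its item 1 then says: "The patient will still be followed in the usual way at the end of their time in hospital". Item 2 has similar wording, and section 11 speaks of in-hospital outcome.

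**The concern.** A status fixed at 28 days needs an observation at or after 28 days. The window in footnote a allows a participant to complete all required follow-up before then. The item 1.2 rationale expects most patients to be managed outside hospital, so the flexible window would apply to most of the trial.

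The secondary endpoints are the most exposed. A complication, admission or death after an early final visit has no required visit at which to be recorded, yet the analysis would report a 28-day proportion. These endpoints are in the hierarchical testing order of section 13.

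The window also depends on discharge. If a treatment shortens hospital stay, more of its recipients move from a fixed Day 28 visit to one that may be a week earlier, and fewer of their late events would be seen. That would favour the treatment for a reason unrelated to its effect on those events.

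For the primary endpoint, the blank lesion cell means that the schedule does not ask for the assessment that the endpoint definition calls for.

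**Working it through.** **1. The plan's own figure.** The one related number is the 372 participants with documented resolution by day 28 (section 13, Number of participants). Inputs there: rate ratio 1.4, 90% power and a 2.5% false positive rate, read as one-sided. Allocation against the shared placebo is 1:1 (section 12). By Schoenfeld's formula:

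d = 4(z₀.₉₇₅ + z₀.₉₀)² / (ln 1.4)² = 4(1.960 + 1.2816)² / (0.3365)² ≈ 371.3, rounded up to 372.

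The figure reproduces. It is a required event count, and the visit window does not alter it.

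**2. Window against horizon.** Study Day d is d − 1 days after randomization.

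| Study Day | Days after randomization | Position relative to 28 days |
|---|---|---|
| 21 (28 − 7) | 20 | 8 days short |
| 28 | 27 | 1 day short |
| 29 | 28 | at the horizon |
| 35 (28 + 7) | 34 | 6 days past |

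The window has 15 permitted days (21 to 35). Eight of them (21 to 28) come before the horizon. At the earliest visit, 8/28 = 29% of the observation period is still to run.

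**3. What else could supply 28-day status.**
- Day 58 visit: optional, may be by phone, and missing it is not a deviation (section 3, footnote b).
- Core safety reporting: life-threatening SUSARs and SAEs possibly related to treatment; other adverse events need not be reported (section 12, Adverse reaction reporting). An unrelated admission or complication need not appear.
- Deaths in hospital: cause of death is asked after discharge or death in hospital (same section). Deaths elsewhere are not covered by this.
- Interim visits: symptoms and adverse events are marked in the interim column, and section 12 (Current symptoms) includes bacterial complications. The column states no end day.

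None of these is a required contact at or after 28 days.

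**4. Lesion status.** If assessments every 3 to 5 days run to the horizon, an unresolved participant is last assessed no more than about 5 days before it. If they stop at an early final visit, the gap can reach 8 days. The endpoint definition and footnote e support the first reading. The schedule names no end day and leaves the 28±7 cell blank.

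**The case against.** The strongest reply concerns the primary endpoint. Its definition, footnote d and footnote e together keep an unresolved participant under assessment every 3 to 5 days, so lesion status does not rest on the Day 28 visit. A reader might infer from the blank cell that lesions go unassessed near day 28; the documents do not support that. The cell conflicts with the endpoint text, and it should be confirmed in the original typeset table, where column alignment is certain. Neighbouring rows read consistently.

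A reader might also infer a loss of events and power. That does not follow. The 372 is a required number of documented resolutions, and section 13 says that the sample size needed to reach it is not known. Undocumented resolutions would mean more enrolment, not lower power at 372 events. Any percentage would need assumed healing times and assumed loss rates that the protocol does not give.

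A third tempting reading is that participants who stop drug are followed no further than hospital discharge. The heading and lead sentence of section 10 say otherwise, and section 11 restricts reporting to the withdrawal date only for those who also refuse further data. What stands is that the later phrases are tied to a hospital stay and fit outpatients poorly.

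It is also fair to say that the early window does not apply to those still in hospital, and that the difference between Study Day 28 and 28 days after randomization is one day, small beside a grid of 3 to 5 days.

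These replies leave the secondary endpoints largely unanswered. Complication collection is expressly tied to day 28, and interim visits are only a partial back-up while their end is unstated.

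**Conclusion.** The point holds for the 28-day secondary endpoints and, to a lesser degree, for the schedule's treatment of the primary endpoint. As written, a compliant final visit can fall 8 days before the horizon for outpatients and for participants discharged before Day 28. Complications in that interval can be missed, mortality and admission have no later required visit to secure them, and completeness depends on an event after randomization.

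The size is an exposed interval of up to 8 of 28 days per participant. How many events fall in it cannot be computed from the protocol, and any bias between arms depends on whether treatment changes time to discharge, which is not known. For the primary endpoint the effect is limited if the interim assessments run to 28 days. The blank lesion cell is an inconsistency to correct, subject to confirmation in the original. The wording of sections 10 and 11 is a secondary matter of clarity.

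**What to change.** 1. In section 3, footnote a, remove the early side of the window, so that the final visit, or a status contact, falls no earlier than 28 days after randomization (Study Day 29 by the protocol's numbering). Apply the same day count to participants still in hospital.
2. At that visit or contact, ascertain vital status, admission, complications and lesion status as of 28 days, with event dates, so that a visit up to Day 35 does not count later events.
3. Mark Lesion Assessment in the 28±7 column, adjusted to the new window.
4. State in the schedule that assessments every 3 to 5 days run to resolution or 28 days after randomization.
5. Reconcile the hospital-based follow-up phrases in sections 10 and 11 with section 10's own rule that participants who stop drug are still followed for outcomes, so that it plainly covers outpatients and discharged participants.

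The cost is wording and schedule edits to a visit that already exists. Some final visits move later by about a week (at most 8 days, from Study Day 21 to 29). If the late limit stays at Day 35, the window narrows from 15 permitted days to 7, which sites may find harder to meet; a status contact eases this for vital status and admission.
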